5.2.1 Mean and Mean Changes Over Time

Mean values (SD) for the mSOFA and for the 5 specific organ components will be summarized over time with and without last-observation-carried-forward (LOCF). Similarly, mean (SD) changes scores from both day 0 and day 1 will be summarized with and without LOCF.

5.2.2 mSOFA as Part of Primary Endpoint

The primary efficacy endpoint (NICCE) employs mSOFA in two of its five components. NICCE success requires mSOFA at Day $14 \le 1$ and the improvement from screening Day 0 to Day 14 that is ≥ 3 .

5.2.3 Time to Organ Dysfunction Resolution

Time to organ dysfunction resolution will be evaluated as a time-to-event endpoint. This will be assessed in descriptive analyses using survival and life-table methods and calculated from time of drug administration. Organ dysfunction resolution will be defined as mSOFA score ≤ 1 . Two analyses will be performed. The first corresponds to the primary efficacy endpoint and evaluates time to mSOFA score ≤ 1 censoring at Day 14. The second extends the follow-up range to Day 28 using available observed mSOFA.

¹⁰ Kaplan EL and Meier P. Nonparametric estimation from incomplete observations, Journal of the American Statistical Association 1959, 53:457-481.

5.2.4 Mixed Models for Repeated Measures (MMRM)

Supporting longitudinal analyses comparing mSOFA means and mean changes over time will be implemented using mixed models for repeated measures (MMRM). The analysis set for the MMRM will not include LOCF imputation. Methods for this approach are described below.

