5.1 Baseline Comparisons

Demographic and baseline characteristics will be summarized for each analysis set overall and by treatment group. Categorical variables including race, ethnicity, and gender will be summarized by counts and percentages. Continuous variables will be summarized using mean, median, standard deviation (SD), and minimum and maximum values. Continuous variables evaluated will include age, BMI, height, weight, systolic BP, diastolic BP, MAP, heart rate, and temperature; as well as ANAYA, LRINEC, and APACHE II scores. Presence of baseline sepsis will be summarized according to the numbers and percentages of patients with baseline cardiovascular and respiratory organ failure as reflected in screening component SOFA scores of 3 or 4. In addition presence of any AKI at baseline algorithmically determined, Stage 2/3 AKI at screening, and maximal AKI Stage 2/3 as assigned by the blinded adjudication panel will be summarized.

Analyses will be performed to confirm that the randomization resulted in no clinically significant group differences at baseline. Although emphasis will be on clinical significance, baseline comparisons will include t-tests or Wilcoxon rank-sum tests as appropriate for interval variables and chi-square or Fisher's exact tests as appropriate for nominal variables to aid in the screening for baseline differences. If there are clinically important baseline differences, multiple logistic regression will be used in supporting analyses to assess the impact of the imbalance on significance levels.

5.2 mSOFA

The Sequential Organ Failure Assessment score or SOFA was originally developed to track a patient's status during a stay in an intensive care unit (ICU)⁸,⁹. Each of six organ systems are evaluated (see Appendix 5) with ordinal scores 0 to 4. A total score is the sum of the component scores. For this study, the liver component is excluded and the resulting sum score is referred to in this study as 'mSOFA'.

Several approaches will be taken to summarize changes over time and between treatment groups in the clinical scores as described below.

mSOFA scores will be assessed as 1) observed cases, 2) last observation carried forward (LOCF), 3) using MMRM, and 4) categorized and combined with mortality and local activity as part of the primary composite clinical success endpoint, NICCE.

The following will be defined as OBSERVED mSOFA.

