1. If a single individual organ score is missing but other scores for that day are non-missing, the organ system that were not evaluated are assumed to be free of organ failure and are given a value of zero when determining the sum score.

⁸ Vincent JL, Moreno R, Takala J, et al: The SOFA (Sepsis-related Organ Failure Assessment) score to describe organ dysfunction failure: On behalf of the Working Group on Sepsis-Related Problems of the European Society of Intensive Care Medicine. Intensive Care Med 1996; 22:707–710.

⁹ Vincent JL, Angus DC, Artigas A, Kalis A, Basson BR, Jamal HH, Johnson III G., Bernard GR for the PROWESS Study Group. Effects of drotrecogin alfa (activated) on organ dysfunction in the PROWESS trial. Crit Care Med 2003; 31:834 – 840.

2. If two or more individual organ scores are missing for mSOFA on Day 14 or earlier, but at least one individual organ score is non-missing, the individual organ scores will be imputed using last observation carried forward. In this case, it is possible that different components come from different visits. This will not be done at Day 21 and Day 28.

The following will defined mSOFA LOCF.

- 3. If all organ scores are missing on Day 14 or earlier, the mSOFA total score from that day will be imputed using last observation carried forward with the following exception.
 - a. LOCF will not be performed after patient death.
 - b. Note that LOCF will not be performed for unavailable mSOFA total scores at Day 21 and Day 28.
- 4. When summarizing the individual organ scores apart from the mSOFA total scores, the same rules as above will apply.
- 5. Patients with recorded screening mSOFA inflated by GCS scores due to mechanical ventilation or due medications will have their GCS score removed when determining screening mSOFA. This is to prevent subjects meeting trial inclusion just on the basis of GCS.

Since LOCF will not be applied to missing mSOFA scores after patient death in analyses that employ LOCF to describe mean values of time, there may be some 'diminishing n' and focus is therefore on morbidity rather than mortality.

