5.10.3 Mixed Model Repeated Measures

The use of MMRM is another method used to address missing data and is considered an optimal approach in many settings. The use of MMRM results in implicit imputations for missing data which are valid under missing at random (MAR), a more general set of assumptions than 'missing completely at random (MCAR)'. For these analyses, there will be implicit imputation of expected mSOFA after patient death. Methods assuming Not Missing at Random (NMAR) require extensive modelling and sensitivity analyses regarding inherently untestable assumptions concerning the missingness mechanism; and will not be used in these analyses.

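### The mSOFA score that the SAP calls observed already carries organ scores forward through Day 14, so the MMRM and the 'observed cases' tables appear to contain LOCF values that SAP 5.2.4 and 8.6 say are absent

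*SAP*

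**What the plan says.** SAP 5.2.4, on the MMRM for mSOFA: "The analysis set for the MMRM will not include LOCF imputation". SAP 5.2.1 promises mean scores and mean changes both with and without LOCF. SAP 8.6 says that Table 14.2.2.3 (change from Day 0) is made without LOCF. Appendix 1 labels Tables 14.2.2.1, 14.2.2.3, 14.2.2.5, 14.2.2.7 and 14.2.2.8 as observed cases.

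The score itself is defined in SAP 5.2, and the rules below are repeated in 5.10.1. Under the lead-in "The following will be defined as OBSERVED mSOFA" there are two rules:

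- Rule 1, one organ score missing: "the organ system that were not evaluated are assumed to be free of organ failure and are given a value of zero".
- Rule 2, for visits through Day 14 at which two or more are absent: "but at least one individual organ score is non-missing, the individual organ scores will be imputed using last observation carried forward". The SAP notes that components may then come from different visits, and adds: "This will not be done at Day 21 and Day 28".

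A second version, mSOFA LOCF, adds rule 3 for visits with no organ score at all: "If all organ scores are missing on Day 14 or earlier, the mSOFA total score from that day will be imputed using last observation". This fill is not made after death or at Days 21 and 28. Rule 4 extends the same rules to summaries of individual organ scores.

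Appendix 4 gives Table 14.2.2.1 as the data source for Figure 17 (MMRM means) and Table 14.2.2.3 for Figure 18 (MMRM mean changes).

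**The concern.** SAP 5.8 prefers the MMRM partly because it avoids assigning values arbitrarily as LOCF does, and 5.8 and 5.10.3 rest its validity on missing at random. That argument covers only values left missing in the data. An organ score filled before modelling enters the likelihood as if measured at that visit, so the missing-at-random machinery never acts on it.

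Rule 2 applies at Day 14, the contrast that 5.8 singles out. If carried-forward components sit inside the MMRM and the observed-cases tables, these analyses are less independent of LOCF than the SAP claims. Their agreement with the LOCF tables would then be partly built in.

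**Working it through.** No figure in the plan is in dispute, so the check compares definitions and then applies them to an example.

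**Step 1: when the two versions differ.** mSOFA has five components. By number missing at a visit on Day 14 or earlier:

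| Organ scores missing | Observed mSOFA | mSOFA LOCF |
|---|---|---|
| 0 | measured total | same |
| 1 | missing organ set to 0 | same |
| 2 to 4 | missing organs carried forward | same |
| 5 | no value | total carried forward |

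Within a visit the versions part only when all five scores are missing. In the 2-to-4 row, the version labelled observed is itself an LOCF score.

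**Step 2: an invented patient.** The values are assumed, for illustration only. Previous visit: respiratory 2, cardiovascular 0, renal 1, coagulation 0, CNS 1, total 2 + 0 + 1 + 0 + 1 = 4. At the next visit, on Day 14 or earlier:

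- (a) Respiratory missing; the others measured as cardiovascular 0, renal 1, coagulation 0, CNS 0. Observed total = 0 (filled) + 0 + 1 + 0 + 0 = 1.
- (b) Respiratory and CNS missing; cardiovascular 0, renal 1, coagulation 0 measured. Observed total = 2 (carried) + 0 + 1 + 0 + 1 (carried) = 4, of which 2 + 1 = 3 points are carried forward.
- (c) Only renal measured, at 1. Observed total = 2 + 0 + 1 + 0 + 1 = 4, with four of the five components carried forward.
- (d) All five missing. No observed value; mSOFA LOCF gives 4.

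In (b) and (c) a total labelled observed is mostly carried forward. If rule 2 were not applied, (a) would stay at 1 and (b), (c) and (d) would all be missing.

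**Step 3: which version reaches the MMRM.** SAP 5.2 and 5.10.1 define two versions only. The figure list ties both MMRM figures to observed-cases tables. The natural reading is that the MMRM runs on observed mSOFA, rule 2 included. This is an inference, because no sentence in 5.2.4 or 5.8 names the input variable.

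**Step 4: reach.** Rule 2 stops at Day 14. At Days 21 and 28 neither component-level nor total-score LOCF is applied. Rule 1 has no day limit, and no rule is given there for two or more missing organs.

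**The case against.** The strongest reply is that 5.2.4 can be read without contradiction. SAP 5.2 and 5.10.1 list observed cases, LOCF and MMRM as separate approaches. So 5.2.4 may be literally true, with a dataset free of all LOCF, or it may exclude only the defined mSOFA LOCF version, that is, rule 3. Both readings are possible. But the SAP states neither, and under the second the MMRM still contains carried-forward components. A programmer could build either dataset. Nor does this reply rescue the observed-cases label or the no-LOCF description of Table 14.2.2.3.

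It is also fair to say that the rules are disclosed, twice, with a warning that components may come from different visits. A reader might infer that the zero fill also breaches 5.2.4. It does not: zero fill is not LOCF, and Protocol 9.2.11.2 gives it openly as the convention for an unmeasured component. The conflict is with rule 2 alone.

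A reader might further infer that carried-forward totals will be common at Day 14, because Protocol 4.3.7 allows telephone follow-up. The documents do not support a frequency. The same section asks for SOFA parameters on the day of an early discharge, and Protocol 4.3 provides visiting nurses from Day 10. A telephone contact might also leave all five scores missing, and rule 2 would then not apply. For Table 14.2.2.7, limited to screening and 16 to 24 hours after dosing, discharge is not a plausible route.

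Finally, requiring all five components would discard visits with four measured scores and depart from the protocol's convention. If organs go unmeasured because the patient is well, it could also strain missing at random. That objection stands, so a complete-component rule belongs in a sensitivity analysis and not in the main MMRM.

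**Conclusion.** The SAP is inconsistent as it stands. Rule 2 places component-level LOCF inside the score called observed, while 5.2.4 and 8.6 say that analyses apparently built on that score contain no LOCF. For the tables through Day 14 this follows from the SAP's own definition and labels. For the MMRM it rests on the figure list and on there being no third version of the score.

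Materiality is low. The MMRM is a supporting analysis, and SAP 5.6 and 5.7 treat these secondary endpoints as descriptive, without type 1 error control. A reader might infer that the primary result is compromised; it is not. NICCE uses LOCF openly (SAP 5.10.1), and neither the conditional co-primary nor the key secondary endpoint uses mSOFA. Nor does every mSOFA analysis depend on LOCF, since Days 21 and 28 are free of it. The numerical effect and its direction between arms cannot be estimated, because the documents do not say how many visits will have two to four organ scores missing.

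**What to change.** 1. State in 5.2.4 and 5.8 which mSOFA variable is the MMRM outcome.
2. For that outcome and for the observed-cases tables, do not apply rule 2: set the total to missing when two or more organ scores are missing at the visit. For the organ-specific rows, amend rule 4 so that missing organ scores are not carried forward either.
3. The single-missing-equals-zero convention may stay. Add an MMRM restricted to totals with all five components measured as a sensitivity analysis.
4. Keep rules 1 and 2 for NICCE and the LOCF tables.
5. Day 1 mSOFA is an MMRM covariate (5.8). State how an incomplete Day 1 score is handled, so that patients are not dropped from the model by default.
6. Report the number of partly measured visits by arm and visit.

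The cost is SAP wording, one derived variable and one sensitivity run. Somewhat fewer totals will enter the MMRM, and its Day 14 score can differ from the one used in NICCE; a footnote should say so.

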5.3 Assessment of poolability among sites

Site poolability for the primary and co-primary endpoints will be evaluated using a random effects meta-analysis approach using the R package *metafor* to implement the analysis 11. True effects will be evaluated on the logit scale and are assumed to be normally distributed with mean μ and variance τ^2 . By imposing a specified distribution on the site-to-site variability, i.e. a normal distribution with mean μ and variance τ^2 , sensitivity to small sample sizes in individual sites is reduced and the parameters reflecting the magnitude of site-to-site variability are naturally derived. The quantitative measure of the magnitude of heterogeneity is I^{2} 12 is the fraction of τ^2 that is due to effect size heterogeneity (among sites), as opposed to sampling variance (within site). Fractions 25% and less are considered small (see references). If there is significant site to site variability, the impact on this variability will be evaluated using a random effects logistic regression to test the null hypothesis that the likelihood of achieving NICCE is the same for treated and placebo patients accounting for site-to-site heterogeneity in treatment effects.

5.4 Analyses Accounting for Stratification Factors

As noted above, randomization will be within site stratified by presence (+) of a diagnosis of Fournier's Gangrene versus absence (-) and whether the screening mSOFA score is >4 (+) or 3-4 (-). An unadjusted chi-square test using a two-sided type 1 error of α =0.01 will be used to test superiority of Reltecimod relative to placebo for the primary endpoint (NICCE). The corresponding 99% confidence interval will be determined.

Analyses will be performed to evaluate the potential impact of the stratification factors (presence versus absence of Fournier's gangrene and screening mSOFA equal to 3-4 versus >4). The estimated overall treatment group difference controlling for these two stratification factors, the stratum adjusted significance level for testing the superiority hypothesis, and the corresponding 95% confidence interval for the group difference in Month 24 CCS will be determined using a generalized linear model. The model covariates are treatment group and a categorical variable (df=3) for randomization stratum. The model parameters will be estimated using SAS Proc Genmod with distribution set to *binomial* and link set to *logit*. The stratum adjusted success rates and standard errors of the success rates are determined on the probability scale using the *ilink* option in a *Ismeans* statement with a *diff* option. This statement produces a stratum adjusted significance level. The standard error on the probability scale for the difference in NICCE success rates needed for the 99% confidence interval will be determined as the square root of the sum of the device group specific standard errors which are generated as part of model estimation. The significance level for the stratum by treatment group difference interaction will be reported from a model in which the interaction is added. Within stratum differences and 95% confidence intervals will be summarized in descriptive analyses.

¹¹ Viechtbauer W. Bias and efficiency of meta-analytic variance estimators in the random-effects model. J Educ Behav Stat. 2005;30(3):261-293.

¹² Higgins JP, Thompson SG, Deeks JJ. Altman DG. Measuring inconsistency in meta-analyses. BMJ: 327(7414):557

The goal of the stratified randomization is to promote good balance of the stratification factors within site between the two treatment groups. It is possible that subjects will be assigned to a randomization stratum in error. If there are any subjects that are assigned to the incorrect stratum, then these analyses will be repeated using the subjects' true stratification status. To this end, significance levels and relative success rates with confidence intervals will be determined and compared for the primary and conditional co-primary endpoints for three scenarios. These three scenarios are:

- 1) Not accounting for stratified randomization (primary),
- 2) control for the actual stratification using a generalized linear model, and
- 3) control for strata defined based on actual subject status using a generalized linear model.

For example, if a subject was identified with a diagnosis of Fournier's Gangrene but it is later discovered that the subject actually did not actually have Fournier's Gangrene, then this subject would be moved into the correct stratum in scenario 3. In addition to the overall summary measures across strata, results within strata for scenarios 2 and 3 will be summarized.

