2.4 Sample Size Justification

2.4.1 Primary Endpoint

This trial will enroll 290 subjects that will be randomized in a ratio of 1:1 to either Reltecimod 0.50 mg/kg (n=145) or placebo (n=145), each in addition to standard of care. Sample size analysis was performed assuming that all patients will be evaluable for the primary endpoint. This assumption is justified on the basis of results from the Phase 2a trial and the Retrospective Study in which all patients were evaluable in terms of the definitions used to construct the NICCE endpoint.

The primary efficacy hypothesis will be tested using an unadjusted χ^2 statistic with an α =0.01 two-sided significance level. Statistical power was computed for a range of expected treatment group differences supported by the results of the preliminary studies noted above. For expected treatment group differences of 0.30, 0.25, and 0.20, statistical power will be 99%, 95.9%, and 80.2%, respectively. These power determinations were conservatively made assuming an average success rate between treatment groups of 0.5. In this way power estimates are applicable across the range of expected response rates; but may be conservative in some cases.

The use of NICCE and this range of expected treatment effects is supported by preliminary studies as summarized in the following table.

	Percentage Achieving NICCE	(n/N)
Phase 2a (mSOFA≥3) Reltecimod 0.50 mg/kg	71.4%	(5/7)
Phase 2a (mSOFA≥3) Placebo	20.0%	(1/5)
Retrospective Study (mSOFA≥3)	30.4%	(21/69)

In the Phase 2a trial, 71.4% (5/7) patients with baseline mSOFA≥3 treated with Reltecimod (at a dose of 0.50 mg/kg) achieved NICCE. In contrast, only 20% (1/5) of placebo patients with baseline mSOFA≥3 achieved NICCE, a difference of 51.4%. The Retrospective Study provides further support for the untreated response rate. Among 69 patients with baseline mSOFA≥3, 30.4% (21/69) achieved NICCE, a difference of 41.0% relative to Phase 2a patients in the 0.50 mg/kg treated group presenting with screening mSOFA≥3.

Given the selected sample sizes, if the observed differences in this study happen to be equal to 35%, 25%, or 20% (centered about 50%), then the corresponding 2-sided p-values will be

p<0.0001, p<0.0001, and p=0.0007, respectively. The observed difference will need to be larger than about 16% (e.g., 58% vs 42%) for p \le 0.01 (again assuming that the average success rate between groups is 50%).

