8.4 Evaluation of Stratification Factors

Table 14.2.1.7.1 summarizes the numbers and percentages of subjects achieving the NICCE within each level of the randomized stratification. The generalized linear model stratum adjusted risk difference, 99% confidence interval, and the adjusted p-value is presented for comparison to primary unadjusted results. A test for stratum by treatment group interaction will also be presented.

Table 14.2.1.7.2 provides the same analysis but based on the true stratification status. If there are no subjects that were placed in the incorrect stratum, this table will not be produced.

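### The SAP's stratum-adjusted risk difference is a difference of back-transformed average logits, which in general is not the population risk difference it is set beside

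*SAP*

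**What the plan says.** The confirmatory NICCE analysis is unadjusted. SAP 5.4 states: "An unadjusted chi-square test using a two-sided type 1 error of" 0.01.

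The same section then plans a supportive analysis for the two stratification factors, Fournier's gangrene and screening mSOFA 3-4 versus >4. "The model covariates are treatment group and a categorical variable (df=3) for randomization stratum", and the model is binomial with a logit link, fitted in Proc Genmod. For the estimates, "The stratum adjusted success rates and standard errors of the success rates are determined on the probability scale" with the ilink option of an lsmeans statement. No observed-margins option or other weighting is named. The formula for the difference is not written out. However, its standard error is built from the two group-specific standard errors on the probability scale, so a difference of the two back-transformed rates is the only reading offered.

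SAP 8.4 states the purpose of Table 14.2.1.7.1: "The generalized linear model stratum adjusted risk difference, 99% confidence interval, and the adjusted p-value is presented for comparison to primary unadjusted results". That table covers NICCE only. The closing part of SAP 5.4 plans the same comparison of unadjusted and stratum-controlled results for the conditional co-primary endpoint (CCPE).

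**The concern.** The unadjusted difference estimates the difference in success rates in the trial population. An LS-mean from a main-effects logit model is built differently. The four stratum logits are averaged, with 25% weight each by default, and the average is then back-transformed. That gives the success probability at an average logit, not the average success probability. The two agree when the strata do not predict outcome and generally differ when they do.

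Prognostic strata are plausible here: screening mSOFA is a stratification factor, and Day 14 mSOFA is part of NICCE. A reader who sees two different numbers would put the gap down to adjustment for stratum imbalance, yet it can arise with perfectly balanced arms.

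**Working it through.** **Inputs from the documents.** 145 patients per arm, two-sided alpha 0.01 and a retrospective NICCE rate of 30.4% (21/69) are in SAP 2.4.1. The 46.6% share with mSOFA >4 is in SAP 2.5.

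**Inputs assumed.** Stratum shares are 42/36/12/10% for 3-4 without Fournier's, >4 without, 3-4 with, and >4 with. This puts 36 + 10 = 46% above 4 and 22% with Fournier's. The common odds ratio is 2.25, so b = ln 2.25 = 0.811. Stratum control rates are varied.

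**The plan's own figures.** The SAP states no value for the adjusted difference. Its power figures can be checked. With d centred on 0.5, power = Φ[(d − 2.576·√(0.5/145)) / √((p1q1 + p0q0)/145)]. For d = 0.20 this is Φ[(0.200 − 0.151)/0.0575] = 80.2%. For 0.25 and 0.30 it is 95.9% and 99.6%, in line with SAP 2.4.1.

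**Formulas.** Population difference = Σ w_k(p1k − p0k), with logit p1k = logit p0k + b. LS-mean difference = expit(m + b) − expit(m), where m is the plain mean of the four control logits.

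**One case in full.** Control rates are 0.40/0.20/0.45/0.25.
- Active rates are 0.600/0.360/0.648/0.429.
- Overall rates are 0.319 and 0.502, so the population difference is 0.183.
- Control logits are −0.405, −1.386, −0.201 and −1.099, so m = −0.773.
- LS-mean difference = expit(0.038) − expit(−0.773) = 0.510 − 0.316 = 0.194.

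| Assumed control rates | Overall control | Population | LS-mean | Gap | LS-mean, observed margins |
|---|---|---|---|---|---|
| 0.40/0.20/0.45/0.25 | 0.319 | 0.183 | 0.194 | +0.01 | 0.193 |
| 0.45/0.15/0.50/0.20 | 0.323 | 0.171 | 0.192 | +0.02 | 0.191 |
| 0.60/0.20/0.65/0.25 | 0.427 | 0.166 | 0.200 | +0.03 | 0.200 |
| 0.40/0.30/0.15/0.05 | 0.299 | 0.174 | 0.153 | −0.02 | 0.185 |

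**Cause.** In the first three rows, weighting the logits by stratum share changes the result by at most 0.001, so logit averaging produces almost all of the gap. In the fourth row, equal weights pull the reference logit towards two small, low-rate strata and reverse the sign. With share weights the mean logit is 0.42(−0.405) + 0.36(−0.847) + 0.12(−1.735) + 0.10(−2.944) = −0.978. The difference is then expit(−0.167) − expit(−0.978) = 0.458 − 0.273 = 0.185, which still misses 0.174.

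**Wider range.** Across 20,000 assumed settings (base control rate 0.25-0.45, Fournier's share 5-50%, odds ratio 2.3) the gap had median +0.019 and range −0.014 to +0.056. It was positive in 96% and negative in about 4%. These shares describe the assumed grid, not the trial.

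**Finite samples.** In 1,500 simulated trials of 290 patients, with control rates of 0.25 (mSOFA >4) and 0.55 (3-4) and 20% Fournier's, the mean unadjusted difference was 0.201. The logistic model standardised over the stratum mix also averaged 0.201, and the SAP's LS-mean difference averaged 0.224.

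**Null.** If b = 0, both expressions are zero.

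**The case against.** The strongest reply is that nothing confirmatory depends on this estimate. The primary test is unadjusted and has its own difference and 99% interval. Study success rests on p-values (SAP 2.2). The model's p-value tests the log odds ratio, which back-transformation does not touch. All of that stands.

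The size is also modest. In the first two rows the standard error of an unadjusted difference with 145 per arm is about 0.057. The gaps are then about 0.18 and 0.37 standard errors, or 7% and 14% of a 99% half-width of 0.146. That stands too.

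Readers also get counts and percentages by stratum (SAP 8.4), from which they could work out a size-weighted difference. This helps a careful reader, but it does not make the labelled estimate right.

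The same paragraph of SAP 5.4 has a larger, separate fault: it takes the square root of the sum of the standard errors rather than of their squares. Correcting that alone would put a proper interval around the same mismatched point estimate.

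A reader might infer that the method always inflates the effect. The fourth row shows that it need not. The third row (+20% in relative terms) might be taken as the expected size. Its control rate of 0.427 is well above the 30.4% and 20% that SAP 2.4.1 cites, and it assumes a 40-point spread between the mSOFA strata, for which the documents give no support.

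**Conclusion.** The point holds for a supportive estimate. As specified, the adjusted figure is not in general the population risk difference with which SAP 8.4 invites comparison. With a control rate near 0.30 and an odds ratio of 2.25, the gap is about +0.01 to +0.02 in typical assumed cases, mainly from averaging on the logit scale. It is about −0.02 if small Fournier's strata do very poorly, and zero if the strata are not prognostic or there is no treatment effect. These sizes rest on assumed stratum rates and an assumed Fournier's share. The reading also assumes default LS-mean weights, because no others are named. The documents do not support a claim that the primary result, the success rule or the adjusted p-value is biased.

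**What to change.** In SAP 5.4 and 8.4, replace the LS-mean difference with one of two estimates:
- The logistic model standardised over all mITT patients: average the predicted probabilities with everyone set to each arm in turn, and take the difference. Use a delta-method or bootstrap 99% interval.
- A Mantel-Haenszel stratum-weighted risk difference with its matching variance.

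Apply the same change to the CCPE comparison at the end of SAP 5.4, with a 95% interval. Adding only an observed-margins option would not be enough, because the averaging would still be on the logit scale. If the logit-scale p-value is kept, label it as the test of the adjusted odds ratio, since it can disagree with a risk-difference interval near the threshold.

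The cost is a short SAP revision and a few lines of code, which can be done before unblinding. The primary analysis does not change.

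### SAP 5.4 forms the SE of the stratum-adjusted NICCE difference from unsquared standard errors, so the supportive 99% CI would be about five times too wide

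*SAP*

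**What the plan says.** The primary analysis of NICCE is an unadjusted chi-square test at two-sided 0.01 with a 99% confidence interval (SAP 2.1.2). SAP 5.4 adds a supportive analysis that controls for Fournier's gangrene and screening mSOFA category. It is a binomial model with logit link, treatment and a four-level stratum variable. From the least-squares-means output, the "standard errors of the success rates are determined on the probability scale". Of the same output the SAP says: "This statement produces a stratum adjusted significance level". The SE of the difference is then to be built by hand: it "will be determined as the square root of the sum of the device group specific standard errors".

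SAP 8.4 sends the result to Table 14.2.1.7.1: "The generalized linear model stratum adjusted risk difference, 99% confidence interval, and the adjusted p-value is presented for comparison to primary unadjusted results".

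SAP 5.4 also asks that "significance levels and relative success rates with confidence intervals will be determined and compared for the primary and conditional co-primary endpoints", under three ways of handling the strata.

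The same paragraph carries wording that does not belong to this trial. It refers to device groups, and it calls for the "corresponding 95% confidence interval for the group difference in Month 24 CCS will be determined using a generalized linear model". The protocol's last visit is at 3 months, and the later sentence of 5.4 and SAP 8.4 both give 99% for NICCE.

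**The concern.** The quantities taken from the model are standard errors, not variances. The variance of a difference is the sum of the two variances less twice the covariance. The square root of a sum of unsquared standard errors is therefore not a standard error of anything. A scale check shows this: with arm SEs of 4.07 percentage points the rule gives √8.14 = 2.85 points, about half the correct 5.75. With the same SEs written as proportions it gives 0.285, about five times the correct value. SAP 5.4 specifies the probability scale, so the fivefold inflation is what the text would produce.

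The analysis exists to show whether accounting for stratification changes the primary result. Table 14.2.1.7.1 would place a very wide interval covering zero beside an adjusted p-value that may be below 0.01 and beside a much narrower unadjusted interval. A reader could wrongly conclude that the adjustment removes the precision of the primary result.

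**Working it through.** **Inputs.** 145 patients per arm, two-sided α = 0.01 for NICCE, design differences 0.30, 0.25 and 0.20 with rates centred on 0.5, all patients evaluable (SAP 2.4.1). z = 2.5758 for 99% and 1.960 for 95%.

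**The plan's own figures.** The SAP gives no numerical SE for the adjusted analysis, so the check on inputs is its power statement. Power = Φ[(d − z√(0.5/145)) / √((p₁q₁ + p₂q₂)/145)]. For d = 0.20 this is Φ[(0.20 − 0.1513)/0.0575] = 80.2%. For 0.25 it is 95.9% and for 0.30 it is 99.6%. The SAP states 80.2%, 95.9% and 99%, so the inputs are right.

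**The two rules.** Arm SE: s = √(pq/145). Correct, ignoring covariance: √(s₁² + s₂²). As written: √(s₁ + s₂). These are crude binomial SEs standing in for the model-based ones.

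For 0.60 against 0.40:
- s = √(0.24/145) = 0.0407 in each arm
- correct SE = √(2 × 0.0407²) = 0.0575; 99% half-width 2.5758 × 0.0575 = 0.148
- written SE = √(0.0407 + 0.0407) = 0.285; 99% half-width 2.5758 × 0.285 = 0.735
- ratio 4.96. With equal arm SEs the ratio is 1/√s, so the rule gets worse as the arms get larger.

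| Rates | Correct SE | Written SE | Ratio | Correct 99% CI | Written 99% CI |
|---|---|---|---|---|---|
| 0.58 / 0.42 | 0.0580 | 0.2863 | 4.94 | 0.011 to 0.309 | −0.577 to 0.897 |
| 0.60 / 0.40 | 0.0575 | 0.2853 | 4.96 | 0.052 to 0.348 | −0.535 to 0.935 |
| 0.625 / 0.375 | 0.0569 | 0.2836 | 4.99 | 0.104 to 0.396 | −0.480 to 0.980 |
| 0.65 / 0.35 | 0.0560 | 0.2815 | 5.02 | 0.156 to 0.444 | −0.425 to 1.025 |

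The first row is the SAP's own borderline example, where the unadjusted p is 0.0064. In the last row the upper limit exceeds 1, which a risk difference cannot do.

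**Difference needed to exclude zero.** Solving d = z × SE with rates centred on 0.5 gives about 0.65 under the written rule and 0.15 under the correct one.

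**The SAP's model.** The logit model with treatment and four strata was simulated at a true difference of about 0.20: nine scenarios of 400 trials, with equal-weight adjusted rates transformed back to probabilities. The share with mSOFA above 4 was 46.6% (SAP 2.5). The rest was assumed: Fournier's share 20%, 30% or 40%; log-odds effect of mSOFA above 4 of −0.5, −1.0 or −1.5; Fournier's effect +0.3.
- Written SE 0.288 to 0.315; delta-method SE with covariance 0.058 to 0.062; ratio 4.8 to 5.3.
- The adjusted p was at or below 0.01 in 69% to 84% of trials. The written interval excluded zero in none of the 3,600.
- The sum of squares without covariance exceeded the delta-method SE by about 1%, 5% and 14% at Fournier's shares of 40%, 30% and 20%.

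A second simulation with other assumed strata gave a ratio of 4.9 to 5.0 and a covariance effect of 3% to 4%.

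**CCPE, only if the rule were carried over.** At 0.80 against 0.60 the arm SEs are 0.0332 and 0.0407. The correct SE is 0.0525 (95% half-width 0.103) and the written SE is 0.272 (0.533), a ratio of 5.2.

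**The case against.** The strongest reply is that this is a missing word in a supportive analysis. No confirmatory decision uses this SE, and the adjusted p-value comes straight from the model output. A statistician seeing an interval with an upper limit above 1 would probably catch it. The SAP contains no code for this step, so no wrong interval has been shown to exist. All of this is fair. It limits the consequence but does not make the stated rule right. A programmer who follows the text gets the wrong interval. One who corrects it departs from the SAP, and section 5.12 then requires the deviation to be described and justified. Nor can the protocol supply the correction: it gives no such rule, and SAP section 1 says the SAP prevails where the two differ.

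Three narrower points also stand. The closed-form figures use crude binomial SEs, not adjusted ones; the simulated adjusted SEs are slightly larger, and the factor stays near five. The SE sentence names NICCE only, so the CCPE figure is conditional. The simulation rests on assumed stratum shares and effects, but the main result needs only the arithmetic above.

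**Conclusion.** The concern holds. As written, the rule inflates the SE of the stratum-adjusted NICCE difference about fivefold at the planned size: 4.9 to 5.0 by closed form across the tabulated rates, and 4.8 to 5.3 in simulations of the SAP's model. The supportive 99% interval would cover zero at every design difference. This assumes 145 evaluable patients per arm and literal implementation of the text. It should be corrected before unblinding, but it does not threaten the trial's confirmatory conclusions. The leftover endpoint and device wording and the 95%/99% mismatch are copy-edits that would not justify a comment alone; SAP 8.4 already settles 99% for NICCE.

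**What to change.** In SAP 5.4, define the SE of the adjusted difference as √(SE₁² + SE₂²) or, preferably, as the delta-method SE √(SE₁² + SE₂² − 2·Cov), where Cov is the covariance of the two adjusted rates on the probability scale. The two rates share the stratum coefficients, so the second form is the better one, though the gain is small beside the present error. A stratum-standardised or Mantel-Haenszel risk difference would also serve but is not needed.

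In the same edit:
- name NICCE with a 99% interval, and CCPE with 95%, in place of the leftover endpoint
- change device to treatment
- state that the same SE rule applies to the adjusted CCPE analysis, and name the table that will show it, since Tables 14.2.1.7.1 and 14.2.1.7.2 cover NICCE only

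The p-value is on the log-odds scale and the interval on the probability scale, so a table footnote should say that the two can differ slightly near the boundary even with the correct SE.

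The cost is one or two sentences of SAP text, the footnote and a few lines of code. Data collection, sample size and the primary analysis do not change.
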